1. PROTOCOL SUMMARY

1.1 Synopsis

Rationale for Proposed Clinical Study

The SARS Coronavirus 2 (SARS-CoV-2) pandemic has continued to intensify and as of January 30, 2021, there are over 102 million cases and over 2 million deaths globally (Center for Systems Science and Engineering (CSSE) at Johns Hopkins University [systems.jhu.edu]).

ModernaTX, Inc has developed a messenger RNA (mRNA)-based vaccine platform based on the principle and observations that antigens can be produced *in vivo* by delivery and uptake of the corresponding mRNA by cells. ModernaTX, Inc used its mRNA-based technology to develop a novel lipid nanoparticle (LNP)-encapsulated mRNA-based vaccine encoding for the spike (S) protein of the original Wuhan-Hu-1 isolate of SARS-CoV-2 (mRNA-1273) and in 2020 initiated Phase 1, Phase 2, and Phase 3 trials of a two-dose schedule of this vaccine, given 28 days apart, in adults, in the United States (Jackson LA et al, 2020; Anderson EJ et al, 2020; Widge AT et al, 2020; Baden LR et al, 2020). The Phase 3 trial demonstrated 94.1% efficacy against symptomatic confirmed Coronavirus Disease 2019 (COVID-19) 14 days or later after the second vaccination and 100% efficacy against severe COVID-19 (Baden LR et al, 2020). On December 18, 2020 the U.S. Food and Drug Administration issued an emergency use authorization (EUA) for administration of the vaccine to adults in the United States.

Recently, SARS-CoV-2 variants with mutations in the S protein have emerged. A variant first identified in South Africa (B.1.351) is associated with increased transmission, higher viral burden, and possibly increased mortality in infected persons (Tegally H et al, 2020). To date, four SARS-CoV-2 vaccines, all based on the Wuhan-sequence of the S protein, have shown reduced activity against the B.1.351 variant (Wang P et al, 2021; Wu K et al, 2021). Sera from individuals vaccinated with mRNA-based vaccines had a 6-to-9-fold reduction in neutralizing activity against a B.1.351-matched pseudovirion relative to a Wuhan-matched pseudovirion. More recently, pivotal vaccine efficacy studies testing both viral vector and adjuvanted protein vaccines had lower efficacy in regions where B.1.351 was known to be circulating (Callaway E & Mallapaty S, 2021; Cohen J, 2021).

There is an urgent need for vaccination strategies that induce broader protection that includes variants such as B.1.351 to decrease morbidity and mortality and reduce SARS-CoV-2 transmission. ModernaTX, Inc, is developing a mRNA vaccine (mRNA-1273.351) that is similar to the mRNA-1273 vaccine available under the EUA, but in which the mRNA encodes for the S protein of the B.1.351 variant.

This phase 1 clinical trial will evaluate the safety and immunogenicity of varying doses of mRNA-1273.351, given in vaccination schedules alone, in sequences with mRNA-1273, or as a combination vaccine that includes mRNA-1273, in adults 18 years of age and older who are either naïve to SARS-CoV-2 (have no history of COVID-19 disease or vaccination) or who have been previously vaccinated with mRNA-1273.

Study Design

This is a phase 1, open-label, randomized clinical trial in males and non-pregnant females, 18 years of age and older, who are in good health, have no known history of COVID-19 or SARS-CoV-2 infection, and meet all other eligibility criteria. This clinical trial is designed to assess the

safety, reactogenicity and immunogenicity of mRNA-1273.351 manufactured by ModernaTX, Inc, given in vaccination schedules alone, sequentially, or coadministered with mRNA-1273. mRNA-1273.351 is a novel LNP-encapsulated mRNA-based vaccine that encodes for a full-length, prefusion stabilized S protein of the SARS-CoV-2 B.1.351 variant. Enrollment will occur at approximately five domestic clinical research sites.

This study includes two cohorts. Cohort 1 will provide rapid information about the immunogenicity of mRNA-1273.351 in a previously vaccinated group. This cohort can inform near term public health decisions if the variant virus becomes more widespread. Cohort 2 will evaluate different strategies for generation of cross protective immune responses in a naïve population. This cohort will take longer to provide information on the immunogenicity of mRNA-1273.351, but is important to inform future public health strategies. As Cohorts 1 and 2 are in different populations, they can be enrolled in parallel as determined by each site.

Cohort 1 will include subjects 18 years of age and older who received two vaccinations of mRNA-1273 at dosages of 50 mcg, 100 mcg, or 250 mcg in the Phase 1 clinical trial (DMID 20-0003). Those subjects will be offered enrollment into this study approximately 9 to 12 months after they received the second vaccination in DMID 20-0003. At enrollment in this study, their long-term follow-up in DMID 20-0003 will be terminated. Subjects will be randomized, within each of the DMID 20-0003 cohorts (age and dosage groups – 50 mcg, 100 mcg, and 250 mcg), 1:1 (as outlined in Table 1) to either:

- Arm 1A, vaccination with a 50-mcg dose of the mRNA-1273.351 variant, or
- Arm 1B, vaccination with a combination vaccination that includes 25 mcg of mRNA-1273 and 25 mcg of mRNA-1273.351.

The anticipated sample size to be drawn from the DMID 20-0003 study population is approximately 45 subjects 18 through 55 years of age and approximately 20 subjects 56 years of age and older.

Subjects in Cohort 1 will receive a single intramuscular (IM) injection of the designated vaccine and will be followed through 12 months after vaccination. Follow-up visits will occur on Days 8, 15, and 29, as well as 3, 6, and 12 months after the vaccination.

Table 1. Cohort 1 Treatment Arms

Arm	Sample Size	Vaccination Product and Dose
1A	~30	50 mcg mRNA-1273.351
1B	~30	25 mcg mRNA-1273 + 25 mcg mRNA-1273.351

Cohort 2 will include approximately 150 participants 18 through 55 years of age who have not received a COVID-19 vaccine, have no known history of COVID-19 or SARS-CoV-2 infection, and do not have underlying conditions that are associated with an increased risk of severe illness from SARS-CoV-2 infection. Enrollment may close before the full 150 participants based on estimates on the timing of immunogenicity results and the need to inform public health decisions. They will be randomly assigned to one of 8 treatment arms and will receive 2 or 3 IM injections of the vaccine (as outlined in Table 2), and followed through 12 months after the last

vaccination. Follow-up visits will occur 7, 14, and 28 days after each vaccination, as well as 3, 6 and 12 months post the last vaccination.

Table 2: Cohort 2 Treatment Arms

Arm	Sample Size	First Vaccination	Second Vaccination		Third Vaccination	
		Product and Dose	Interval	Product and Dose	Interval	Product and Dose
2A	15	100 mcg mRNA-1273	28 days	100 mcg mRNA-1273	28 days	50 mcg mRNA-1273.351
2B	15	50 mcg mRNA-1273	28 days	50 mcg mRNA-1273	28 days	50 mcg mRNA-1273.351
2C	20	100 mcg mRNA-1273.351	28 days	100 mcg mRNA-1273.351		None
2D	20	50 mcg mRNA-1273.351	28 days	50 mcg mRNA-1273.351		None
2E	20	100 mcg mRNA-1273	28 days	100 mcg mRNA-1273.351		None
2F	20	50 mcg mRNA-1273	28 days	50 mcg mRNA-1273.351		None
2G	20	50 mcg mRNA-1273 + 50 mcg mRNA-1273.351	28 days	50 mcg mRNA-1273 + 50 mcg mRNA-1273.351		None
2H	20	25 mcg mRNA-1273 + 25 mcg mRNA-1273.351	28 days	25 mcg mRNA-1273 + 25 mcg mRNA-1273.351		None

Summary of Treatment Arms:

- 2A: Evaluates the mRNA1273 EUA vaccination series, plus a variant vaccine as a third dose.
- 2B: Evaluates a 50-mcg vaccination series, plus a variant vaccine as a third dose.
- 2C-2D: Evaluate 2 doses of the homologous variant vaccine at different dose levels.
- 2E-2F: Evaluate heterologous prime-boost strategies at 2 dose levels.
- 2G-2H: Evaluate a 1:1 mix of vaccine (2 doses), with the total dose for both vaccines equal to 100 mcg and 50 mcg, respectively.

For both Cohorts 1 and 2, reactogenicity will be assessed at the above-mentioned visits and blood will be drawn for immunogenicity assays.

Objectives

- **Primary:** To evaluate the safety and reactogenicity of mRNA-1273 and mRNA-1273.351 vaccines, in naïve and previously vaccinated individuals.
- **Secondary:** To assess humoral immunogenicity of mRNA-1273 and mRNA-1273.351 vaccines, in naïve and previously vaccinated individuals.

Inclusion Criteria

See inclusion criteria in [Section 5.1](#).

Exclusion Criteria

See exclusion criteria in [Section 5.2](#).

Study Phase

- 1

Study Population

- Cohort 1, approximately 60 males and non-pregnant females 18 years of age and older, who are in good health and received two vaccinations of mRNA-1273 at dosages of 50 mcg, 100 mcg or 250 mcg in DMID 20-0003.
- Cohort 2, approximately 150 males and non-pregnant females, 18 through 55 years of age, who are in good health.

Sites

- Approximately five domestic clinical research sites.

Study Intervention:

- mRNA-1273 (0.2 milligrams [mg]/mL)
- mRNA-1273.351 (0.5 mg/mL)
- Each vaccine formulation will be diluted in 0.9% Sodium Chloride (NaCl) for injection, United States Pharmacopeia (USP).
- Each dose will be administered via IM injection into the deltoid muscle.
- For Cohort 2, Arms 2A-H, the second dose of vaccine will be administered preferably in the same arm used for the first dose.
- For Cohort 2, Arms 2A and 2B, the third dose of vaccine will also be administered preferably in the same arm used for the first dose.

Study Duration

- The study duration is anticipated to be approximately 17 months (from start of screening through last subject last visit).

Subject Duration

- The duration for each individual subject in Cohort 1 (from first contact to last visit) is approximately 13 months.
- The duration for each individual subject in Cohort 2 (from first contact to last visit) is approximately:
 - 15 months for Arms 2A and 2B.
 - 14 months for Arms 2C through 2H.

Safety

- The study will use pausing rules for vaccinations in the study overall and for not administering second or third vaccinations to individual subjects. See [Section 7.1](#) for details.
- This study will use a Safety Monitoring Committee (SMC) for objective oversight of the study. SMC reviews are required for study halting.

1.2 Schedule of Activities (SOA)

Table 3: SOA for Cohort 1 (One Vaccination)

Study Day	-42 to -1	1	8*	15	29	91	181	366	Unscheduled Visit	Early Termination Visit
Visit Window (\pm number of days)		0	1	2	2	7	7	14		
Study Visit	Screening (optional) 00	01	02	03	04	05	06	07		
Informed Consent	X	X ^a								
Review Eligibility Criteria	X	X								
Medical History	X	X ^a								
Vaccination		X								
Concomitant Medications		X	X	X	X					
Interim History		X ^b		X	X	X	X	X	X	X
Symptom-Directed Physical Examination	X	X		X	X	X	X	X	X	X
Vital Signs ^c		X		X	X	X	X	X	X	X
Height and Weight (for BMI)	X	X ^a								
Pregnancy Test ^d		X								
Memory Aid: Solicited AEs		X	X	X ^e						
Unsolicited AEs		X	X	X	X				X	X
SAEs, Protocol Specified AESIs, MAAEs, and NOCMCs		X	X	X	X	X	X	X		X
Serum for Serological Immunogenicity Assays		X		X	X	X	X	X		X
Peripheral Blood Mononuclear Cells (PBMCs) for Cellular Immunology Assays (and Plasma)		X		X			X	X		X

* Telephone call.

- a) If not performed at Visit 00.
- b) If medical history performed at Visit 00, then interim history at Visit 01.
- c) Vital signs to be obtained pre and post vaccination. Otherwise, only as clinically indicated.
- d) For women of childbearing potential, a negative urine pregnancy test on Day 1 with results confirmed prior to enrollment.
- e) Collect Memory Aid and assess for delayed onset local reactions.

Table 4: SOA for Cohort 2: 2A-B (Three Vaccinations)

Study Day	-42 to -1	1	8*	15	29	36*	43	57	64*	71	85	147	237	422	Unsc Visit	Early Term Visit
Visit Window (\pm number of days)		0	1	2	2	1	2	2	1	2	2	7	7	14		
Study Visit	Screening (optional) 00	01	02	03	04	05 ^e	06 ^e	07 ^e	08 ^f	09 ^f	10 ^f	11 ^f	12 ^f	13 ^f		
Informed Consent	X	X ^a														
Review Eligibility Criteria	X	X														
Medical History	X	X ^a														
Vaccination	X			X			X									
Concomitant Medications		X	X	X	X	X	X	X	X	X	X					
Interim History		X ^b		X	X		X	X		X	X	X	X	X	X	X
Symptom-Directed Physical Examination	X	X		X	X		X	X		X	X	X	X	X	X	X
Vital Signs ^c		X		X	X		X	X		X	X	X	X	X	X	X
Height and Weight (for BMI)	X	X ^a														
Pregnancy Test ^d		X			X			X								
Memory Aid: Solicited AEs		X	X	X ^g	X	X	X ^g	X	X	X ^g						
Unsolicited AEs		X	X	X	X	X	X	X	X	X	X					
SAEs, Protocol Specified AESIs, MAAEs, and NOCMCs		X	X	X	X	X	X	X	X	X	X	X	X	X	X	X
Serum for Serological Immunogenicity Assays		X		X	X		X	X		X	X	X	X			X
Peripheral Blood Mononuclear Cells (PBMCs) for Cellular Immunology Assays (and Plasma)		X		X	X		X	X		X			X	X		X

* Telephone call.

- If not performed at Visit 00.
- If medical history performed at Visit 00, then interim history at Visit 01.
- Vital signs to be obtained pre and post vaccination. Otherwise, only as clinically indicated.
- For women of childbearing potential, a negative urine pregnancy test on Day 1 with results confirmed prior to enrollment.
- Visits 05-07 windows should be based off the actual Visit 04 date.
- Visits 08-13 windows should be based off the actual Visit 07 date.
- Collect Memory Aid and assess for delayed onset local reactions.

Table 5: SOA for Cohort 2: 2C-H (Two Vaccinations)

Study Day	-42 to -1	1	8*	15	29	36*	43	57	119	209	394	Unsc Visit	Early Term Visit
Visit Window (\pm number of days)		0	1	2	2	1	2	2	7	7	14		
Study Visit	Screening (optional) 00	01	02	03	04	05 ^e	06 ^e	07 ^e	08 ^e	09 ^e	10 ^e		
Informed Consent	X	X ^a											
Review Eligibility Criteria	X	X											
Medical History	X	X ^a											
Vaccination		X			X								
Concomitant Medications		X	X	X	X	X	X	X					
Interim History		X ^b		X	X		X	X	X	X	X	X	X
Symptom-Directed Physical Examination	X	X		X	X		X	X	X	X	X	X	X
Vital Signs ^c		X		X	X		X	X	X	X	X	X	X
Height and Weight (for BMI)	X	X ^a											
Pregnancy Test ^d		X			X								
Memory Aid: Solicited AEs		X	X	X ^f	X	X	X ^f						
Unsolicited AEs		X	X	X	X	X	X	X					
SAEs, Protocol Specified AESIs, MAAEs, and NOCMCs		X	X	X	X	X	X	X	X	X	X	X	X
Serum for Serological Immunogenicity Assays		X		X	X		X	X	X	X			X
Peripheral Blood Mononuclear Cells (PBMCs) for Cellular Immunology Assays (and Plasma)			X		X	X		X		X	X		X

* Telephone call.

- If not performed at Visit 00.
- If medical history performed at Visit 00, then interim history at Visit 01.
- Vital signs to be obtained pre and post vaccination. Otherwise, only as clinically indicated.
- For women of childbearing potential, a negative urine pregnancy test on Day 1 with results confirmed prior to enrollment.
- Visits 05-10 windows should be based off the actual Visit 04 date.
- Collect Memory Aid and assess for delayed onset local reactions.

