3. OBJECTIVES AND ENDPOINTS

Table 6: Objectives and Endpoints (Outcome Measures)

OBJECTIVES	ENDPOINTS (OUTCOME MEASURES)
Primary	

To evaluate the safety and reactogenicity of mRNA-1273 and mRNA-1273.351 vaccines, in naïve and previously vaccinated individuals.	
Frequency and grade of each solicited local and systemic reactogenicity AE during a 7-day follow-up period post each vaccination.Frequency and grade of any unsolicited AEs during the 28-day follow-up period post each vaccination.Frequency of any SAEs, Protocol Specified AESIs, NOCMCs, and MAAEs

OBJECTIVES	ENDPOINTS (OUTCOME MEASURES)
	from the first vaccination through 12 months after the last vaccination.
Secondary	

To assess humoral immunogenicity of mRNA-1273 and mRNA-1273.351 vaccines, in naïve and previously vaccinated individuals.	
Response rate, and magnitude of SARS-CoV-2-specific antibody binding and neutralization titers in serum samples as assessed via a range of assays at all timepoints.
Exploratory	

To assess, in at least a subset of samples the innate immune response and B cell response following vaccination.	
Magnitude, phenotype, and percentage of innate immune cells and SARS-CoV-2 specific B cells, as measured by flow cytometry, and targeted B cell repertoire analysis at different timepoints post vaccination relative to baseline.

To assess, in at least a subset of samples, the SARS-CoV-2 S protein-specific T cell responses.	
Magnitude, phenotype, and percentage of cytokine producing S protein-specific T cells, as measured by flow cytometry at different timepoints post vaccination relative to baseline.

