Subjects in Cohort 1 will receive a single intramuscular (IM) injection of the designated vaccine and will be followed through 12 months after vaccination. Follow-up visits will occur on Days 8, 15, and 29, as well as 3, 6, and 12 months after the vaccination.

Table 7. Cohort 1 Treatment Arms

Arm	Sample Size	Vaccination Product and Dose
1A	~30	50 mcg mRNA-1273.351
1B	~30	25 mcg mRNA-1273 + 25 mcg mRNA-1273.351

Cohort 2 will include approximately 150 participants 18 through 55 years of age who have not received a COVID-19 vaccine, have no known history of COVID-19 or SARS-CoV-2 infection, and do not have underlying conditions that are associated with an increased risk of severe illness from SARS-CoV-2 infection. Enrollment may close before the full 150 participants based on estimates on the timing of immunogenicity results and the need to inform public health decisions. They will be randomly assigned to one of 8 treatment arms and will receive 2 or 3 IM injections of the vaccine (as outlined in Table 8), and followed through 12 months after the last vaccination. Follow-up visits will occur 7, 14, and 28 days after each vaccination, as well as 3, 6, and 12 months post the last vaccination.

Table 8: Cohort 2 Treatment Arms

Arm	Sample Size	First Vaccination	Second Vaccination		Third Vaccination	
		Product and Dose	Interval	Product and Dose	Interval	Product and Dose
2A	15	100 mcg mRNA-1273	28 days	100 mcg mRNA-1273	28 days	50 mcg mRNA-1273.351
2B	15	50 mcg mRNA-1273	28 days	50 mcg mRNA-1273	28 days	50 mcg mRNA-1273.351
2C	20	100 mcg mRNA-1273.351	28 days	100 mcg mRNA-1273.351		None
2D	20	50 mcg mRNA-1273.351	28 days	50 mcg mRNA-1273.351		None
2E	20	100 mcg mRNA-1273	28 days	100 mcg mRNA-1273.351		None
2F	20	50 mcg mRNA-1273	28 days	50 mcg mRNA-1273.351		None
2G	20	50 mcg mRNA-1273 + 50 mcg mRNA-1273.351	28 days	50 mcg mRNA-1273 + 50 mcg mRNA-1273.351		None
2H	20	25 mcg mRNA-1273 + 25 mcg mRNA-1273.351	28 days	25 mcg mRNA-1273 + 25 mcg mRNA-1273.351		None

Summary of Treatment Arms:

- 2A: Evaluates the mRNA1273 EUA vaccination series, plus a variant vaccine as a third dose.
- 2B: Evaluates a 50-mcg vaccination series, plus a variant vaccine as a third dose.
- 2C-2D: Evaluate 2 doses of the homologous variant vaccine at different dose levels.
- 2E-2F: Evaluate heterologous prime-boost strategies at 2 dose levels.
- 2G-2H: Evaluate a 1:1 mix of vaccine (2 doses), with the total dose for both vaccines equal to 100 mcg and 50 mcg, respectively.

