8.2 Safety and Other Assessments

Study procedures are specified in the SOA. A study clinician, licensed to make medical diagnoses and listed on the Form FDA 1572 as the participating site PI or appropriate sub-investigator, will be responsible for all study-related medical decisions.

- Medical history:
 - A complete medical history will be obtained by interview of subjects at the screening (optional) or enrollment/baseline visit. Subjects will be queried regarding a history of significant medical disorders.
 - At all subsequent visits an interim medical history will be obtained by interview of subjects and any changes since the previous clinic visit or telephone call will be noted. The interim medical history should include an assessment to identify intercurrent Protocol Specified AESIs, MAAEs, and NOCMCs.
- Physical examination:
 - A symptom-directed (targeted) physical examination will be performed if indicated at any timepoint at the discretion of the participating site PI or appropriate sub-investigator, if necessary, to evaluate AEs.

- Reactogenicity assessments of solicited AEs occurring from the time of vaccination through 7 days post vaccination, will include an assessment of injection site reactions—erythema, edema/induration and pain, as well as systemic reactions—fever, fatigue, chills, myalgia (exclusive of the injection site), arthralgia, headache, and nausea. Pre-administration reactogenicity assessments will be performed immediately prior to each vaccination to establish baseline, then the vaccination will be given.
- Subjects will be observed in the clinic for at least 30 minutes post each vaccination. The vaccination site will be examined, post-administration reactogenicity assessments will be performed, and any AEs/SAEs will be recorded on the appropriate DCF prior to discharge from the clinic. The vaccination site will also be examined 7 days after vaccination.
- Vital signs: Vital sign measurements will include systolic and diastolic BP, HR, and oral temperature. Vital signs will be measured at timepoints specified in the SOA. On vaccination days, vital sign measurements will be collected prior to vaccine administration. Vital signs assessed on Day 1 prior to the first vaccination will be considered as baseline. Subjects must not eat or drink anything hot or cold within 10 minutes prior to taking oral temperature.

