Serum for Serological Immunogenicity Assays ¹		16		16	16		16	16		16	16	16	16	16	16 ²	160
PBMCs (and Plasma) for Cellular Immunology Assays		64		48	40		64	40		64			64	64	16 ² or 40 ²	448
Serum for Secondary Research		16		16	16		16	16		16	16	16	16	16	16 ²	160
Per Visit Blood Volume Total (mL)		96		80	72		96	72		96	32	32	96	96		768
Cumulative Blood Volume (mL) (prior 56 days)		96	96	176	248	248	344	416	320	416	368	64	96	96		
Running Blood Volume Total (mL)		96	96	176	248	248	344	416	416	512	544	576	672	768		

¹ Inability (e.g., failure of venipuncture) to collect all baseline samples on Day 1 will not exclude the subject from further participation in this study as long as a minimum of baseline blood volume is collected.

² These blood volumes are not included in the blood volume totals. Blood volume depends upon day of early termination visit.

³ Visits 05-07 windows should be based off the actual Visit 04 date.

⁴ Visits 08-13 windows should be based off the actual Visit 07 date.

Table 11: Venipuncture Volumes for Cohort 2: 2C-H (Two Vaccinations)

Study Day	-42 to -1	1	8	15	29	36	43	57	119	209	394	Early Term Visit	Total Volume of Blood Drawn (mL)
Visit Window (\pm number of days)		0	1	2	2	1	2	2	7	7	14		
Study Visit	Screening (optional) 00	01	02	03	04	05 ³	06 ³	07 ³	08 ³	09 ³	10 ³		
Vaccination		X			X								
Serum for Serological Immunogenicity Assays ¹		16		16	16		16	16	16	16	16	16 ²	128
PBMCs (and Plasma) for Cellular Immunology Assays		64		48	40		64			64	64	16 ² or 40 ²	344
Serum for Secondary Research		16		16	16		16	16	16	16	16	16 ²	128
Per Visit Blood Volume Total (mL)		96		80	72		96	32	32	96	96		600
Cumulative Blood Volume (mL) (prior 56 days)		96	96	176	248	248	344	376	64	96	96		
Running Blood Volume Total (mL)		96	96	176	248	248	344	376	408	504	600		

¹ Inability (e.g., failure of venipuncture) to collect all baseline samples on Day 1 will not exclude the subject from further participation in this study as long as a minimum of baseline blood volume is collected.

² These blood volumes are not included in the blood volume totals. Blood volume depends upon day of early termination visit.

³ Visits 05-10 windows should be based off the actual Visit 04 date.

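### The Cohort 2 Schedules of Activities leave the 12-month serology draw blank, while the venipuncture tables schedule it and count it in their totals

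*Protocol*

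**What the plan says.** Three parts of the protocol bear on the 12-month serum sample in Cohort 2.

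- **SOA, Section 1.2.** In Table 4 the row "Serum for Serological Immunogenicity Assays" is marked on Days 1, 15, 29, 43, 57, 71, 85, 147 and 237 and at early termination. Day 422 is blank. In Table 5 the row is marked on Days 1, 15, 29, 43, 57, 119 and 209 and at early termination. Day 394 is blank. In both tables the PBMC row does have a mark at the 12-month visit.
- **Venipuncture tables, Section 8.2.** Table 10 lists 16 mL of assay serum at ten visits, Day 422 included. Table 11 lists 16 mL at eight visits, Day 394 included.
- **Design and endpoint text.** Section 4.1 says of Cohort 2: "Follow-up visits will occur 7, 14, and 28 days after each vaccination, as well as 3, 6, and 12 months post the last vaccination". It adds that blood for immunogenicity assays is drawn at these visits. The secondary endpoint in Section 3 covers "antibody binding and neutralization titers in serum samples as assessed via a range of assays at all timepoints", and Section 9.4.3 plans seroconversion rates, GMFR and GMT by arm at all timepoints.

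Section 8.2 opens with the statement "Study procedures are specified in the SOA".

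**The concern.** The protocol gives a site two different instructions for the same visit. Section 10.1.10 treats any non-compliance with the protocol as a deviation, so whichever table a site follows, it departs from the other.

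The visit at issue is the last one. In Cohort 2 the serology draws before it are at 3 and 6 months after the last vaccination, so the 12-month draw is the only one later than 6 months. Where it is missed, the by-arm titre summaries for that arm lose subjects at the final timepoint, or end at 6 months. The blank also sits oddly with its surroundings: the SOA keeps the exploratory PBMC sample at 12 months and takes serum from subjects who terminate early, yet shows none from those who complete.

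**Working it through.** **Which visit is blank.** Day 422 is 422 − 57 = 365 days after the third vaccination in Arms 2A-B. Day 394 is 394 − 29 = 365 days after the second vaccination in Arms 2C-H. Both are the 12-month visit.

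**The protocol's own volume totals.** Each serum draw is 16 mL. Total blood is assay serum + PBMC/plasma + secondary-research serum, without early-termination samples.

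- Table 9 (Cohort 1): 6 × 16 = 96; 96 + 256 + 96 = 448 mL, as stated.
- Table 10 (2A-B): 10 × 16 = 160; 160 + 448 + 160 = 768 mL, as stated.
- Table 11 (2C-H): 8 × 16 = 128; 128 + 344 + 128 = 600 mL, as stated.

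The Cohort 2 totals reproduce only with the 12-month assay serum included.

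**Scheduled serology draws, SOA against volume table.**

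| | SOA draws | Volume-table draws | Serum implied by SOA | Serum stated | Total blood implied by SOA | Total stated |
|---|---|---|---|---|---|---|
| Cohort 1 (Tables 3, 9) | 6 | 6 | 96 mL | 96 mL | 448 mL | 448 mL |
| Arms 2A-B (Tables 4, 10) | 9 | 10 | 9 × 16 = 144 mL | 160 mL | 768 − 16 = 752 mL | 768 mL |
| Arms 2C-H (Tables 5, 11) | 7 | 8 | 7 × 16 = 112 mL | 128 mL | 600 − 16 = 584 mL | 600 mL |

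Cohort 1 agrees, and its 12-month serum draw (Day 366) appears in both tables. In Cohort 2 each pair differs by one draw, at the 12-month visit.

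**Could this be a fault in reading the PDF?** A correct number of cells does not settle it. The Table 5 PBMC row, as read, also has 13 cells for 13 columns, yet it places draws on Days 8 and 36, which are telephone contacts. The Table 4 vaccination row is displaced too. But those rows keep their full number of marks: three vaccinations in Table 4, and six PBMC draws plus early termination in Table 5, as in Table 11.

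The serum rows do not. With early termination counted, Table 10 implies 10 + 1 = 11 marks and Table 4 has 10. Table 11 implies 8 + 1 = 9 marks and Table 5 has 8. Moving marks sideways cannot supply the missing one. Both rows also match the volume tables at every earlier visit. A genuine omission is the better reading, though the source PDF should be checked.

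**Number affected.** Arms 2A-B: 2 × 15 = 30. Arms 2C-H: 6 × 20 = 120. Together 150, an upper figure because Section 4.1 allows enrollment to close early.

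**The case against.** A reader might infer that the SOA overrides the other tables and that 12-month antibody data will therefore be lost in every naive subject. The documents do not support that.

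- The opening sentence of Section 8.2 is a general pointer and sets no order of precedence. Tables 9 to 11 stand in the same section, and Section 8.1.2, on immunogenicity sampling, sends the reader to them for the blood to be collected.
- The SOA is not a complete list of samples. It has no row for secondary-research serum, which Tables 9 to 11 draw at every blood-draw visit, so sites need the volume tables in any case.
- Other text points to the draw. Section 4.1 does so in general terms (loosely, since its 7-day contacts are telephone calls). Section 7.1.3 refers to immunogenicity evaluation through 12 months for subjects who stop dosing.
- Both SOA tables still show PBMC and plasma at the 12-month visit, so a venipuncture takes place. Section 10.1.1.2 allows extra or residual serum to serve as back-up.

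These points stand and limit the consequence. The back-up argument is weaker than it looks: secondary-research serum appears only in the volume tables, so a site working from the SOA alone would miss that serum too, while a site using Tables 10 and 11 would already draw the assay serum. Plasma would remain, but the endpoint is defined in serum.

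It is also fair that the endpoint does not name 12 months, that durability is not a separate objective, and that serology is secondary and descriptive, with no hypothesis test (Section 9.1). None of this removes the conflict between the tables.

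**Conclusion.** The contradiction is real. Tables 4 and 5 each show one serology draw fewer than Tables 10 and 11, at the 12-month visit, a difference of 16 mL per subject. It is an internal inconsistency rather than a design decision: Cohort 1 has the draw in both places and nothing in the text cancels it for Cohort 2.

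The exposure is conditional. At sites that schedule from the SOA alone, Cohort 2 would have no assay serum after 6 months, and the secondary endpoint would be weakened at its last timepoint. At sites that use Tables 10 and 11, nothing is lost. Up to about 150 subjects in 8 arms are concerned; the protocol does not show how many sites would schedule in which way. Safety, the primary endpoint, is not affected, and the 3- and 6-month draws remain for describing persistence.

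The conclusion assumes that the blanks are in the source PDF and that the volume tables show what the sponsor intended. The reproduced totals and the Cohort 1 schedule support the second assumption.

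**What to change.** First check the serum rows of Tables 4 and 5 against the source PDF. If the cells are blank there, add an X for serological serum at Visit 13 (Day 422) in Table 4 and at Visit 10 (Day 394) in Table 5, so that both agree with Tables 10 and 11.

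The cost is two table cells in an amendment or clarification letter. The SOA would then give 10 and 8 draws, that is 160 mL and 128 mL of assay serum, with no blood beyond the stated totals of 768 mL and 600 mL. It should reach sites before their first 12-month visit in Cohort 2.
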